#### **12.0 OUTLIERS**

Individual values for the key outcome parameters (body weight, waist circumference, and body composition) at each time point across intervention groups will be examined. Subjects who have values outside  $\pm 1.5 \times \text{IQR}$  will be discussed and decisions about how to handle these data will be agreed upon and documented in writing.

### **13.0. DEVIATIONS FROM STATISTICAL PLAN AND OTHER ISSUES**

During the analysis and reporting process, any deviations from the statistical plan designed for this protocol will be described and justified in the clinical study report.

### **14.0. CHANGES FROM THE PROTOCOL**

#### **1. Analysis populations**

An intent-to-treat (ITT) population will include all participants who were randomized into the study. A complete case population (i.e., completers) will include the subset of participants that completed the study on their assigned intervention. A modified ITT population will include all randomized participants that had a least one post-baseline weight measurement.

#### **Changed to**

*An Intent-To-Treat (ITT) population will include all subjects who were randomized into the study. A modified ITT population will include all randomized participants that had at least one post-baseline weight measurement. In addition, a Completers population will comprise subjects who were randomized into the study and completed all the clinic visits of the whole 16 weeks of the study.*

#### **2. Primary outcome variables**

The primary endpoint is change (percent change and absolute change) from baseline (Visit 2; week 0) body weight to Visit 7 (week 16). Body weight change (percent and absolute change) at Visits 3, 4, 5, and 6 (weeks 2, 4, 8, and 12) will also be evaluated.

#### **Changed to**

*The primary outcome variable will be change (absolute and percent change) in body weight from baseline (Visit 2; week 0) to end of study (Visit 7; week 16)*

#### **3. Secondary outcome variables**

#### **Added**

*Change (absolute and percent change) in body weight from baseline (Visit 2; week 0) to Visits 3, 4, 5, and 6 (weeks 2, 4, 8, and 12)*

*Participation at assigned coaching sessions as a measure of adherence for the TSFL group.*

*Utilization of Nutrition Support for the TSFL and MEDD group.*

#### **4. Missing or Incomplete Data**

Analysis with and without imputation will be conducted in the ITT population. For the analysis with imputation, single [e.g., last observation carried forward (LOCF)], and/or

multiple imputation will be considered, as appropriate (Elobeid, 2009; Peng 2015; George 2016).

#### **Changed to**

*For the ITT population, a multiple imputation method will be implemented if the missing data mechanism is at least missing at random (MAR). Meanwhile, for the modified ITT population, analyses with and without imputation will be conducted. For this imputation, the method of Last Observation Carried Forward (LOCF) will be used as a single imputation approach (Elobeid MA et al, 2009). In this approach, if a subject's measurement is missing at a post-randomization visit, the value from the most proximal prior visit will be used for all missing visits afterwards. The imputation methods will only be applied to body weights. No imputations will be performed for other variables.*

#### 5. Outliers

Individual values for the key outcome parameters (body weight and waist circumference) at each time point across intervention groups will be examined. Subjects who have values outside  $\pm 1.5 \times \text{IQR}$  will be discussed and decisions about how to handle these data will be agreed upon and documented in writing.

#### **Changed to**

*Individual values for the key outcome parameters (body weight, waist circumference, and body composition) at each time point across intervention groups will be examined. Subjects who have values outside  $\pm 1.5 \times \text{IQR}$  will be discussed and decisions about how to handle these data will be agreed upon and documented in writing.*

## 16.0. PLANNED TABLES

The following tables will be produced for the ITT, mITT and Completers populations as appropriate.

### Population(s)

	Table 1	Subject Disposition
ITT	Table 2.1	Demographic Characteristics
ITT	Table 2.2	Vitals
ITT, mITT, Completers	Table 3	Primary Outcome Variable: Body Weight (Visit 7)
ITT, mITT, Completers	Table 4.1	Secondary Outcome Variables: Body Weight (Visits 3, 4, 5, 6)
ITT, mITT, Completers	Table 4.2	Secondary Outcome Variables: Weight Loss $\geq$ 5% and $\geq$ 10%
mITT, Completers	Table 4.3	Secondary Outcome Variables: Body Composition
mITT, Completers	Table 4.4	Secondary Outcome Variables: Body Circumference Parameters
mITT, Completers	Table 4.5	Secondary Outcome Variables: hs-CRP
mITT, Completers	Table 4.6	Secondary Outcome Variable: IWQOL-Lite Questionnaire Outcomes
mITT, Completers	Table 4.7	Secondary Outcome Variable: RAND Health Survey Questionnaire Outcomes
mITT, Completers	Table 4.8.1	Secondary Outcome Variables: Satisfaction and Health/Well-being Questionnaire
mITT, Completers	Table 4.8.2	Secondary Outcome Variables: Satisfaction and Health/Well-being Questionnaire (Recoded)
mITT, Completers	Table 4.9	Secondary Outcome Variables: Program Questionnaire

mITT, Completers	Table 4.10	Secondary Outcome Variable: Weight Loss Program Adherence
mITT, Completers	Table 4.11	Secondary Outcome Variable: Nutrition Support Contact
mITT	Table 5	Summary of Subjects with at Least One Intervention-Emergent Adverse Event

**Note: Tables 3, 4.1, and 4.2 will be generated for Completers, ITT population with multiple imputation applied for the missing data and for the mITT population, both with and without imputation. For the mITT population with imputation, LOCF imputation method applied for missing data will be reflected in footnotes of relevant tables. All other tables generated for the mITT population will be without imputation.**

Table 1  
Subject Disposition

---

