6.7. Early Termination Procedures

The term "Early Termination" refers to a participant's non-completion of the study. Should a participant decide to withdraw, all efforts will be made to complete and report observations as thoroughly as possible. In the event that a participant is withdrawn from the study, the reason for the withdrawal and the party who initiated the withdrawal (participant or Clinical Investigator) will be documented. Should the participant decide to withdraw, documentation of the early termination will be made and an attempt to conduct an early termination visit (which will occur at week 16 and include the clinic visit procedures for Visit 7).

The primary reason for a participant withdrawing prematurely should be selected fiom the following standard categories:

Adverse Event- event which results in discontinuation of the study food by the participant or that in the judgment of the Clinical Investigator for the best interest of the participant requires discontinuation of study food (includes all categories of study food relatedness; Not Related, Unlikely, Possibly, Probably, and Definitely).

Death -death of the participant.

Withdrawal of Consent- participant desires to withdraw from further participation in the study in the absence of a medical need to withdraw determined by the Clinical Investigator.

Lost to Follow-Up- participant did not return for one or more follow-up visit(s) following dispensing of test product and could not be contacted thereafter. The reason for withdrawal was unknown and could not be documented.

Other- causes of premature termination from the study other than the above, such as theft or loss of study foods, pregnancy, termination of study by Sponsor, etc.

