9.2. Adverse Event Monitoring

In a consensus view of guidelines for the design, conduct and reporting of human intervention studies to evaluate the health benefits of foods, an International Life Sciences Institute Europe Expert Group defines an AE as "any untoward medical occurrence or undesirable clinical experience in a participant in a clinical trial, whether or not considered related to the intervention" (Welch 2011). This includes any occurrence that is new in onset or aggravated in severity or frequency from the baseline condition, or abnormal results of diagnostic procedures (including laboratory test abnormalities where applicable). Therefore, clinical observations, including responses to the question, "Have there been in any changes in your health or medications since you were last asked?" will be collected post randomization. These observations will be reviewed for assessment of AE, including severity and potential relationship to the dietary intervention as determined by the study physician.

Events should be considered AEs if they:

- Result in discontinuation from the study,
- Require treatment or any other therapeutic intervention,
- Require further diagnostic evaluation (excluding a repetition of the same procedure to confirm the abnormality),
- Are associated with clinical signs or symptoms judged by the Clinical Investigator to have a significant clinical impact.

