9.2.3. Serious Adverse Event Definition/Qualification

A SAE is defined as an AE that results in any of the following outcomes:

- Death (note that death is the outcome of a SAE and the cause of death should be listed as the AE)
- Life-threatening event
- In-patient hospitalization or prolongation of existing hospitalization
- A persistent or significant disability/incapacity
- Congenital anomaly or birth defect
- Any other important medical event that may not result in death, be life-threatening, or require hospitalization, may be considered a SAE when, based upon appropriate medical judgment, the event may jeopardize the pmlicipant and may require medical or surgical intervention to prevent one of the outcomes listed above. Examples of such medical events include allergic bronchospasm requiring intensive treatment in an emergency room or at home, blood dyscrasias or convulsions that do not result in in-patient hospitalization, or the development of drug dependency or drug abuse.

In the event of a SAE, the participant may be dropped from the study if the Clinical Investigator deems it necessary.

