9.2.5. Electronic CRF Recording of Adverse Events

All AEs will be recorded on the AE eCRF page. For participants who have an ongoing AE at their final study visit, a follow-up AE eCRF page will be collected after 30 d. Participants will be instructed to notify Biofortis Innovation Services immediately should new AEs emerge for an additional 30 d following their last day on the study diet. All SAEs must be recorded on the AE and SAE eCRF page.

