10.5. Withdrawal of Participants from the Study

Participants may be removed from the study for any of the following reasons:

- A participant requests discontinuation;
- The Clinical Investigator initiates removal for medical or compliance reasons;
- Occurrence of any AE or condition that could, in the Clinical Investigator's opinion, interfere with the evaluation of the treatment effect of the study food or put the participant at undue risk.

It is understood by all concerned that an excessive rate of withdrawals can render the study uninterpretable, therefore, unnecessary withdrawal of participants should be avoided. Should a participant decide to withdraw, all efforts will be made to complete and report observations as thoroughly as possible. In the event that a participant is withdrawn from the study, the reason for the withdrawal will be documented in the eCRF. Prior to a participant's withdrawal from the study, an attempt will be made to conduct an early termination visit, which will occur at week 16 and include the clinic visit procedures for Visit 7.

Note that any participant who achieves a BMI of $\leq 19 \text{ kg/m}^2$ will be placed on a weight maintenance diet and should not be withdrawn from the study.

II. Administrative Matters

All references to the Sponsor in this section include all designees e.g., Contract Research Organizations or Consultants acting on behalf of the Sponsor.

Jason Pharmaceuticals, Inc. BI0-1607 (MED 019) 21 June 2016; Version 1.7 Confidential

CANADA CONTRACTOR CONTRACTOR CONTRACTOR CONTRACTOR

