### **5.0. ANALYSIS POPULATIONS**

All statistical analyses will be conducted using SAS® software for Windows (version 9.4 or higher, Cary, NC).

An Intent-To-Treat (ITT) population will include all subjects who were randomized into the study. A modified ITT (mITT) population will include all randomized participants that had at least one post-baseline weight measurement. In addition, a Completers population will comprise subjects who were randomized into the study and completed all clinic visits during the entire 16-week study period.

All decisions regarding population assignment will be documented prior to database lock.

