#### **11.0. SAFETY ANALYSIS**

Safety assessments will be determined from intervention-emergent AEs that occur after randomization at Visit 2 (week 0). Possible differences in the number of participants with at least one AE will be assessed with Chi-Square or Fisher's exact test.

Participants who achieve a BMI of  $19.0 \text{ kg/m}^2$  or below will discontinue the weight loss diet and begin a maintenance diet and will be asked to return for remaining clinic visits. These participants will be noted in the safety analysis.

Vitals (blood pressure, pulse rate) will be summarized by group with descriptive statistics.

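### The only adverse event table is restricted to mITT, so events in randomised participants who are never weighed after baseline drop out of it

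*SAP*

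**What the plan says.** The table list in SAP section 16.0 gives each output its population. Table 5, "Summary of Subjects with at Least One Intervention-Emergent Adverse Event", carries the label mITT and no other. No other listed table or shell summarises AEs. The Table 5 shell has rows for any AE, serious, severe and related events, by group, with p-values.

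SAP section 5.0 defines the population: "A modified ITT (mITT) population will include all randomized participants that had at least one post-baseline weight measurement". ITT, by contrast, is everyone randomised. The SAP defines no separate safety population.

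SAP section 11.0 says: "Safety assessments will be determined from intervention-emergent AEs that occur after randomization at Visit 2 (week 0". Protocol section 8.2.3 has the same sentence. Both say which events count. Neither names a population or sets a condition about weight. Protocol section 9.2.5 adds: "All AEs will be recorded on the AE eCRF page".

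**The concern.** Membership of mITT is settled by an efficacy measurement taken after the intervention has begun. Participants start their programme the day after randomisation, but the first scheduled weight after baseline is at Visit 3. Anyone who has an event in between, leaves, and is not weighed later is outside mITT, so the event is outside Table 5.

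The event can itself cause the exclusion. Protocol section 9.2.3 states: "In the event of a SAE, the participant may be dropped from the study if the Clinical Investigator deems it necessary". Protocol section 10.5 lists among the grounds for removal "Occurrence of any AE or condition that could" interfere with evaluation or put the participant at undue risk. Protocol section 9.2 counts as AEs those events that "Result in discontinuation from the study". The people a safety summary most needs to keep are thus among those it can lose.

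At stake is the trial's only summary of AEs. A reader who sees zero serious events in a group could not tell whether none occurred or one was excluded. Individual SAE reporting and follow-up (Protocol sections 9.2.4 and 9.2.6) are unaffected; the gap is in the summary.

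**Working it through.** **Inputs from the documents**
- Randomised: 198, or 66 per group. Evaluable: 165, or 55 per group (Protocol section 8.1).
- First post-baseline weight: Visit 3, week 2 ± 2 days (Protocol section 6.6.3), which is day 14 ± 2, or day 12 to 16.
- Study length: 16 weeks = 112 days.

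**The plan's own figures.** A two-sample t calculation with a difference of 9.0 lb, SD 15.0 lb, two-sided alpha 0.025 and 80% power gives 54.08, rounded up to 55 per group, as stated. The attrition allowance is 66 − 55 = 11 per group, 198 − 165 = 33 in all, or 16.7%. The point made here does not depend on the power calculation; only the allowance is used.

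**How many might be affected.** The documents do not say when people leave. Assuming even attrition over 112 days, the number leaving before Visit 3 is:
- per group: 11 × 12/112 = 1.2 to 11 × 16/112 = 1.6
- in all: 33 × 12/112 = 3.5 to 33 × 16/112 = 4.7

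This is before any return. Protocol section 6.7 has a termination visit attempted at week 16 with the Visit 7 procedures, and a person weighed then enters mITT.

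**Effect on Table 5.** For a group of 66, let A be the number with an AE, k the number with no post-baseline weight, and j the number of those k with a recorded AE. Then

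ITT rate = A/66; mITT rate = (A − j)/(66 − k).

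The count falls by j and can never rise. The rate falls only if j/k exceeds the AE proportion among those kept, so rates and the group comparison can move either way.

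*Serious events, A = j = k = 1:* 1/66 = 1.5% becomes 0/65 = 0%.

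*Any AE, k = 2, with A assumed to be 10, 20 or 40:*

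| A | ITT rate (A/66) | mITT, j = 2 | mITT, j = 1 | mITT, j = 0 |
|---|---|---|---|---|
| 10 | 15.2% | 8/64 = 12.5% | 9/64 = 14.1% | 10/64 = 15.6% |
| 20 | 30.3% | 18/64 = 28.1% | 19/64 = 29.7% | 20/64 = 31.3% |
| 40 | 60.6% | 38/64 = 59.4% | 39/64 = 60.9% | 40/64 = 62.5% |

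The shift runs from −2.7 points (A = 10, j = 2) to +1.9 points (A = 40, j = 0). With j = 1 it runs from −1.1 to +0.3. With k = 1 it runs from −1.3 (9/65 = 13.8% against 10/66 = 15.2%) to +0.9 (40/65 = 61.5% against 40/66 = 60.6%).

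**Whether another output covers the gap.** The Table 1 shell counts Adverse Event and Death by group, but only as reasons for discontinuation. Protocol section 6.7 asks for one primary reason, so a participant with an AE who is coded as lost to follow-up or as withdrawing consent shows no AE there. Table 1 also gives no seriousness, severity, relatedness or test. Vital signs (Table 2.2) are assigned to ITT, so the plan's two safety outputs use different populations. SAP section 14.0 gives no reason for restricting AEs to mITT.

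**The case against.** The best argument for mITT concerns ascertainment. Every post-baseline visit that includes an AE inquiry also includes a weight, so having a post-baseline weight is close to having been asked about AEs at least once. Under ITT, a person who was never asked again and reported nothing counts as free of AEs. Contact before Visit 3 also differs by group. TSFL has up to 4 + 2 = 6 scheduled coaching calls between day 1 and the end of week 2, whereas MEDD has only discretionary access and Control has none. The documents do not say that coaches record AEs, but reporting by early leavers may be incomplete and uneven. This stands as a limitation. It is a reason to show these people openly, not to remove events already recorded for them.

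It is also fair to say that the safety sections name no population, so the label in section 16.0 contradicts no explicit rule; that several conditions must coincide (early departure, a recorded event, no later weight); and that an event which is the primary reason for leaving appears in Table 1. Applying the assumed AE proportions of 15.2% to 60.6% to 1.2 to 1.6 early leavers gives roughly 0.2 to 1.0 omitted participants with an AE per group, although the AE rate in early leavers is unknown and could be higher. These points limit the size of the problem. They do not restore the lost information on seriousness, severity and relatedness.

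Table 5 has no separate death row under either population. But a death is the outcome of an SAE under Protocol section 9.2.3, so excluding the person removes the event from the any-AE and serious rows.

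**Conclusion.** The concern holds. Followed as written, the plan leaves out of its only AE summary any recorded event in a randomised participant who has no weight after baseline, although its safety sections count events from randomisation without that condition.

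The expected effect is small and could be nil: about one or two early leavers per group under even attrition, fewer if some are weighed at week 16, and shifts of at most about 3 points in the any-AE rate in the examples. Those figures rest on the assumed timing of attrition and the assumed AE proportions, neither of which the documents give. The direction for counts is certain: they can only be too low. For serious events a single exclusion can turn one into none. The change should be made because the exclusion can depend on the event and is easily avoided.

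**What to change.** In SAP section 16.0, change the population for Table 5 from mITT to ITT, presented by assigned group, and name that population in section 11.0. Add a footnote giving, for each group, the number with no clinic visit after baseline and the AEs, SAEs and deaths recorded among them. That shows the reader who had no scheduled AE inquiry. A participant who attended but was not weighed is already counted once the table is on ITT. The mITT version may be kept as a supplement.

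The cost is a population label, a short matching sentence in section 11.0, a footnote and, if the supplement is kept, one repeat of the table. No new data are needed. The drawback is the incomplete and possibly uneven AE reporting among early leavers, which the footnote and the supplement make visible.

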17.0. APPENDIX: TABLE SHELLS

Number of Subjects	Control	TSFL	MEDD	Overall
Screened				N (%)
Randomized	N (%)	N (%)	N (%)	N (%)
Completed Study	N (%)	N (%)	N (%)	N (%)
Did Not Complete Study	N (%)	N (%)	N (%)	N (%)
Included in:				
m ITT Population	N (%)	N (%)	N (%)	N (%)
Completers Population	N (%)	N (%)	N (%)	N (%)
Discontinued due to:				
Adverse Event	N (%)	N (%)	N (%)	N (%)
Death	N (%)	N (%)	N (%)	N (%)
Withdrawal of Consent	N (%)	N (%)	N (%)	N (%)
Lost to Follow-up	N (%)	N (%)	N (%)	N (%)
Other	N (%)	N (%)	N (%)	N (%)

Table 2.1  
Demographic Characteristics

Characteristic		Control (N=)	TSFL (N=)	MEDD (N=)	Overall (N=)	p-value*
Gender	Female	N (%)	N (%)	N (%)	N (%)	x.xxx
	Male	N (%)	N (%)	N (%)	N (%)	
	Total	N (%)	N (%)	N (%)	N (%)	
Age (years)	N	N	N	N	N	x.xxx
	Mean (SEM)	Mean (SEM)	Mean (SEM)	Mean (SEM)	Mean (SEM)	
	Median	Median	Median	Median	Median	
	Q1, Q3	Q1, Q3	Q1, Q3	Q1, Q3	Q1, Q3	
	Min, Max	Min, Max	Min, Max	Min, Max	Min, Max	
Race	White	N (%)	N (%)	N (%)	N (%)	x.xxx
	Black/African American	N (%)	N (%)	N (%)	N (%)	
	American Indian or Pacific Islander	N (%)	N (%)	N (%)	N (%)	
	Multiracial Origin	N (%)	N (%)	N (%)	N (%)	
	Other	N (%)	N (%)	N (%)	N (%)	
	Total	N (%)	N (%)	N (%)	N (%)	
Ethnicity	Non-Hispanic/Latino	N (%)	N (%)	N (%)	N (%)	x.xxx
	Hispanic/Latino	N (%)	N (%)	N (%)	N (%)	
	Total	N (%)	N (%)	N (%)	N (%)	
Weight (kg)	N	N	N	N	N	x.xxx
	Mean (SEM)	Mean (SEM)	Mean (SEM)	Mean (SEM)	Mean (SEM)	
	Median	Median	Median	Median	Median	
	Q1, Q3	Q1, Q3	Q1, Q3	Q1, Q3	Q1, Q3	
	Min, Max	Min, Max	Min, Max	Min, Max	Min, Max	
Height (cm)	N	N	N	N	N	x.xxx
	Mean (SEM)	Mean (SEM)	Mean (SEM)	Mean (SEM)	Mean (SEM)	
	Median	Median	Median	Median	Median	
	Q1, Q3	Q1, Q3	Q1, Q3	Q1, Q3	Q1, Q3	

Table 2.1  
Demographic Characteristics

Characteristic		Control (N = )	TSFL (N=)	MEDD (N=)	Overall (N=)	p-value*
BMI (kg/m  )	Min, Max	Min, Max	Min, Max	Min, Max	Min, Max	
	N	N	N	N	N	x.xxx
	Mean (SEM)	Mean (SEM)	Mean (SEM)	Mean (SEM)	Mean (SEM)	
	Median	Median	Median	Median	Median	
	Q1, Q3	Q1, Q3	Q1, Q3	Q1, Q3	Q1, Q3	
BMI (kg/m  )	Min, Max	Min, Max	Min, Max	Min, Max	Min, Max	
	Overweight (27.00 to 30.00)	N (%)	N (%)	N (%)	N (%)	x.xxx
	Obese (>30.00)	N (%)	N (%)	N (%)	N (%)	
Systolic Blood Pressure (mmHg)	N	N	N	N	N	x.xxx
Systolic Blood Pressure (mmHg)	Mean (SEM)	Mean (SEM)	Mean (SEM)	Mean (SEM)	Mean (SEM)	
	Median	Median	Median	Median	Median	
	Q1, Q3	Q1, Q3	Q1, Q3	Q1, Q3	Q1, Q3	
	Min, Max	Min, Max	Min, Max	Min, Max	Min, Max	
Diastolic Blood Pressure (mmHg)	N	N	N	N	N	x.xxx
Diastolic Blood Pressure (mmHg)	Mean (SEM)	Mean (SEM)	Mean (SEM)	Mean (SEM)	Mean (SEM)	
	Median	Median	Median	Median	Median	
	Q1, Q3	Q1, Q3	Q1, Q3	Q1, Q3	Q1, Q3	
	Min, Max	Min, Max	Min, Max	Min, Max	Min, Max	
Heart Rate (bpm)	N	N	N	N	N	x.xxx
	Mean (SEM)	Mean (SEM)	Mean (SEM)	Mean (SEM)	Mean (SEM)	
	Median	Median	Median	Median	Median	
	Q1, Q3	Q1, Q3	Q1, Q3	Q1, Q3	Q1, Q3	
	Min, Max	Min, Max	Min, Max	Min, Max	Min, Max	
Fasting glucose (mg/dL)	N	N	N	N	N	x.xxx
	Mean (SEM)	Mean (SEM)	Mean (SEM)	Mean (SEM)	Mean (SEM)	
	Median	Median	Median	Median	Median	

Table 2.1  
Demographic Characteristics

Characteristic	Control (N=)	TSFL (N=)	MEDD (N=)	Overall (N=)	p-value*
	Q1, Q3	Q1, Q3	Q1, Q3	Q1, Q3	
	Min, Max	Min, Max	Min, Max	Min, Max	
Smoking Status	Non-Smoker	N (%)	N (%)	N (%)	x.xxx
	Current Smoker	N (%)	N (%)	N (%)	
	Past Smoker	N (%)	N (%)	N (%)	
	Total	N (%)	N (%)	N (%)	
Education	Some High School, no diploma	N (%)	N (%)	N (%)	x.xxx
	High School diploma or equivalent (GED)	N (%)	N (%)	N (%)	
	Trade/Technical/Vocational Training	N (%)	N (%)	N (%)	
	Some College, no degree	N (%)	N (%)	N (%)	
	College Degree (Associate or Bachelor)	N (%)	N (%)	N (%)	
	Graduate/Professional Degree	N (%)	N (%)	N (%)	
	Total	N (%)	N (%)	N (%)	

\*p-values shown are generated from Chi-Square test, Fisher's exact test, or ANOVA, as appropriate

Table 2.2  
Vitals

Parameter	Week		Control (N=)	TSFL (N=)	MEDD (N=)	Overall (N=)
Systolic Blood Pressure (mmHg)	Screening ( Week -1)	N	N	N	N	N
	(Visit 1)	Mean (SEM)	Mean (SEM)	Mean (SEM)	Mean (SEM)	Mean (SEM)
		Median	Median	Median	Median	Median
		Q1, Q3	Q1, Q3	Q1, Q3	Q1, Q3	Q1, Q3
		Min, Max	Min, Max	Min, Max	Min, Max	Min, Max
	Baseline ( Week 0)	N	N	N	N	N
	(Visit 2)	Mean (SEM)	Mean (SEM)	Mean (SEM)	Mean (SEM)	Mean (SEM)
		Median	Median	Median	Median	Median
		Q1, Q3	Q1, Q3	Q1, Q3	Q1, Q3	Q1, Q3
		Min, Max	Min, Max	Min, Max	Min, Max	Min, Max
	Week 2	N	N	N	N	N
	(Visit 3)	Mean (SEM)	Mean (SEM)	Mean (SEM)	Mean (SEM)	Mean (SEM)
		Median	Median	Median	Median	Median
		Q1, Q3	Q1, Q3	Q1, Q3	Q1, Q3	Q1, Q3
		Min, Max	Min, Max	Min, Max	Min, Max	Min, Max
	Week 4	N	N	N	N	N
	(Visit 4)	Mean (SEM)	Mean (SEM)	Mean (SEM)	Mean (SEM)	Mean (SEM)
		Median	Median	Median	Median	Median
		Q1, Q3	Q1, Q3	Q1, Q3	Q1, Q3	Q1, Q3
		Min, Max	Min, Max	Min, Max	Min, Max	Min, Max
	Week 8	N	N	N	N	N
	(Visit 5)	Mean (SEM)	Mean (SEM)	Mean (SEM)	Mean (SEM)	Mean (SEM)
		Median	Median	Median	Median	Median
		Q1, Q3	Q1, Q3	Q1, Q3	Q1, Q3	Q1, Q3
Min, Max		Min, Max	Min, Max	Min, Max	Min, Max	
Week 12	N	N	N	N	N	
(Visit 6)	Mean (SEM)	Mean (SEM)	Mean (SEM)	Mean (SEM)	Mean (SEM)	

Table 2.2  
Vitals

Parameter	Week		Control (N = )	TSFL (N=)	MEDD (N=)	Overall (N=)
		Median	Median	Median	Median	Median
		Q1, Q3	Q1, Q3	Q1, Q3	Q1, Q3	Q1, Q3
		Min, Max	Min, Max	Min, Max	Min, Max	Min, Max
	Week 16	N	N	N	N	N
	(Visit 7)	Mean (SEM)	Mean (SEM)	Mean (SEM)	Mean (SEM)	Mean (SEM)
		Median	Median	Median	Median	Median
		Q1, Q3	Q1, Q3	Q1, Q3	Q1, Q3	Q1, Q3
		Min, Max	Min, Max	Min, Max	Min, Max	Min, Max
Diastolic Blood	Screening ( Week -1)	N	N	N	N	N
Pressure (mmHg)	(Visit 1)	Mean (SEM)	Mean (SEM)	Mean (SEM)	Mean (SEM)	Mean (SEM)
		Median	Median	Median	Median	Median
		Q1, Q3	Q1, Q3	Q1, Q3	Q1, Q3	Q1, Q3
		Min, Max	Min, Max	Min, Max	Min, Max	Min, Max
	Baseline ( Week 0)	N	N	N	N	N
	(Visit 2)	Mean (SEM)	Mean (SEM)	Mean (SEM)	Mean (SEM)	Mean (SEM)
		Median	Median	Median	Median	Median
		Q1, Q3	Q1, Q3	Q1, Q3	Q1, Q3	Q1, Q3
		Min, Max	Min, Max	Min, Max	Min, Max	Min, Max
	Week 2	N	N	N	N	N
	(Visit 3)	Mean (SEM)	Mean (SEM)	Mean (SEM)	Mean (SEM)	Mean (SEM)
		Median	Median	Median	Median	Median
		Q1, Q3	Q1, Q3	Q1, Q3	Q1, Q3	Q1, Q3
		Min, Max	Min, Max	Min, Max	Min, Max	Min, Max
	Week 4	N	N	N	N	N
	(Visit 4)	Mean (SEM)	Mean (SEM)	Mean (SEM)	Mean (SEM)	Mean (SEM)
		Median	Median	Median	Median	Median
		Q1, Q3	Q1, Q3	Q1, Q3	Q1, Q3	Q1, Q3
		Min, Max	Min, Max	Min, Max	Min, Max	Min, Max

Table 2.2  
Vitals

Parameter	Week		Control (N=)	TSFL (N=)	MEDD (N=)	Overall (N=)
	Week 8	N	N	N	N	N
	(Visit 5)	Mean (SEM)	Mean (SEM)	Mean (SEM)	Mean (SEM)	Mean (SEM)
		Median	Median	Median	Median	Median
		Q1, Q3	Q1, Q3	Q1, Q3	Q1, Q3	Q1, Q3
		Min, Max	Min, Max	Min, Max	Min, Max	Min, Max
	Week 12	N	N	N	N	N
	(Visit 6)	Mean (SEM)	Mean (SEM)	Mean (SEM)	Mean (SEM)	Mean (SEM)
		Median	Median	Median	Median	Median
		Q1, Q3	Q1, Q3	Q1, Q3	Q1, Q3	Q1, Q3
		Min, Max	Min, Max	Min, Max	Min, Max	Min, Max
	Week 16	N	N	N	N	N
	(Visit 7)	Mean (SEM)	Mean (SEM)	Mean (SEM)	Mean (SEM)	Mean (SEM)
		Median	Median	Median	Median	Median
		Q1, Q3	Q1, Q3	Q1, Q3	Q1, Q3	Q1, Q3
		Min, Max	Min, Max	Min, Max	Min, Max	Min, Max
Heart Rate (bpm)	Screening ( Week -1)	N	N	N	N	N
	(Visit 1)	Mean (SEM)	Mean (SEM)	Mean (SEM)	Mean (SEM)	Mean (SEM)
		Median	Median	Median	Median	Median
		Q1, Q3	Q1, Q3	Q1, Q3	Q1, Q3	Q1, Q3
		Min, Max	Min, Max	Min, Max	Min, Max	Min, Max
	Baseline ( Week 0)	N	N	N	N	N
	(Visit 2)	Mean (SEM)	Mean (SEM)	Mean (SEM)	Mean (SEM)	Mean (SEM)
		Median	Median	Median	Median	Median
		Q1, Q3	Q1, Q3	Q1, Q3	Q1, Q3	Q1, Q3
		Min, Max	Min, Max	Min, Max	Min, Max	Min, Max
	Week 2	N	N	N	N	N
	(Visit 3)	Mean (SEM)	Mean (SEM)	Mean (SEM)	Mean (SEM)	Mean (SEM)
		Median	Median	Median	Median	Median

Table 2.2  
Vitals

Parameter	Week	Control (N=)	TSFL (N=)	MEDD (N=)	Overall (N=)
		Q1, Q3	Q1, Q3	Q1, Q3	Q1, Q3
		Min, Max	Min, Max	Min, Max	Min, Max
	Week 4	N	N	N	N
	(Visit 4)	Mean (SEM)	Mean (SEM)	Mean (SEM)	Mean (SEM)
		Median	Median	Median	Median
		Q1, Q3	Q1, Q3	Q1, Q3	Q1, Q3
		Min, Max	Min, Max	Min, Max	Min, Max
	Week 8	N	N	N	N
	(Visit 5)	Mean (SEM)	Mean (SEM)	Mean (SEM)	Mean (SEM)
		Median	Median	Median	Median
		Q1, Q3	Q1, Q3	Q1, Q3	Q1, Q3
		Min, Max	Min, Max	Min, Max	Min, Max
	Week 12	N	N	N	N
	(Visit 6)	Mean (SEM)	Mean (SEM)	Mean (SEM)	Mean (SEM)
		Median	Median	Median	Median
		Q1, Q3	Q1, Q3	Q1, Q3	Q1, Q3
		Min, Max	Min, Max	Min, Max	Min, Max
	Week 16	N	N	N	N
	(Visit 7)	Mean (SEM)	Mean (SEM)	Mean (SEM)	Mean (SEM)
		Median	Median	Median	Median
		Q1, Q3	Q1, Q3	Q1, Q3	Q1, Q3
		Min, Max	Min, Max	Min, Max	Min, Max

Table 3  
Primary Outcome Variable: Body Weight (Visit 7) Descriptive Statistics and P-values

Parameter	Week		Control	TSFL	MEDD	Intervention p-value ^	
Body Weight (kg)	Baseline ( Week 0) (Visit 2)	N	N	N	N		
		Mean (SEM)	Mean (SEM)	Mean (SEM)	Mean (SEM)		
		Median	Median	Median	Median		
		Q1, Q3	Q1, Q3	Q1, Q3	Q1, Q3		
		Min, Max	Min, Max	Min, Max	Min, Max		
	Week 16 (Visit 7)	N	N	N	N		
		Mean (SEM)	Mean (SEM)	Mean (SEM)	Mean (SEM)		
		Median	Median	Median	Median		
		Q1, Q3	Q1, Q3	Q1, Q3	Q1, Q3		
		Min, Max	Min, Max	Min, Max	Min, Max		
	Change (Week 16)	N	N	N	N		
		Mean (SEM)	Mean (SEM)	Mean (SEM)	Mean (SEM)		
		Median	Median	Median	Median		
		Q1, Q3	Q1, Q3	Q1, Q3	Q1, Q3		
		Min, Max	Min, Max	Min, Max	Min, Max		
			Within group p-value+	x.xxx(r)	x.xxx(r)	x.xxx(r)	
			LS Mean (SEM)	LS Mean (SEM)	LS Mean (SEM)	LS Mean (SEM)	x.xxx(r)
			Group comparison p-value*		x.xxx(r)	x.xxx(r)	
	% Change (Week 16)	N	N	N	N		
		Mean (SEM)	Mean (SEM)	Mean (SEM)	Mean (SEM)		
Median		Median	Median	Median			
Q1, Q3		Q1, Q3	Q1, Q3	Q1, Q3			
Min, Max		Min, Max	Min, Max	Min, Max			
		Within group p-value+	x.xxx(r)	x.xxx(r)	x.xxx(r)		
		LS Mean (SEM)	LS Mean (SEM)	LS Mean (SEM)	LS Mean (SEM)	x.xxx(r)	
		Group comparison p-value*		x.xxx(r)	x.xxx(r)		

^ p-values are from ANCOVA models, adjusted for sex and baseline values at Visit 2

(r) indicates rank transformation was employed.

\* p-values are adjusted for multiple comparisons (each active group vs. control group)

Table 3  
Primary Outcome Variable: Body Weight (Visit 7) Descriptive Statistics and P-values

---

+ p-values are generated from paired t-test or sign-rank test, as appropriate

Table 4.1  
Secondary Outcome Variable: Body Weight (Visit 3, 4, 5, 6) Descriptive Statistics and P-values

Parameter	Week	Control	TSFL	MEDD	Intervention p-value^		
Body Weight (kg)	Baseline ( Week 0)	N	N	N	N		
	(Visit 2)	Mean (SEM)	Mean (SEM)	Mean (SEM)	Mean (SEM)		
		Median	Median	Median	Median		
		Q1, Q3	Q1, Q3	Q1, Q3	Q1, Q3		
		Min, Max	Min, Max	Min, Max	Min, Max		
		N	N	N	N		
	Week 2 (Visit 3)	Mean (SEM)	Mean (SEM)	Mean (SEM)	Mean (SEM)		
		Median	Median	Median	Median		
		Q1, Q3	Q1, Q3	Q1, Q3	Q1, Q3		
		Min, Max	Min, Max	Min, Max	Min, Max		
		N	N	N	N		
	Change (Week 2)	Mean (SEM)	Mean (SEM)	Mean (SEM)	Mean (SEM)		
		Median	Median	Median	Median		
		Q1, Q3	Q1, Q3	Q1, Q3	Q1, Q3		
		Min, Max	Min, Max	Min, Max	Min, Max		
		Within group p-value+	x.xxx(r)	x.xxx(r)	x.xxx(r)		
		LS Mean (SEM)	LS Mean (SEM)	LS Mean (SEM)	LS Mean (SEM)	x.xxx(r)	
		Group comparison p-value*		x.xxx(r)	x.xxx(r)		
		% Change (Week 2)	N	N	N	N	
			Mean (SEM)	Mean (SEM)	Mean (SEM)	Mean (SEM)	
			Median	Median	Median	Median	
	Q1, Q3		Q1, Q3	Q1, Q3	Q1, Q3		
	Min, Max		Min, Max	Min, Max	Min, Max		
	Within group p-value+		x.xxx(r)	x.xxx(r)	x.xxx(r)		
	LS Mean (SEM)		LS Mean (SEM)	LS Mean (SEM)	LS Mean (SEM)	x.xxx(r)	
	Group comparison p-value*		x.xxx(r)	x.xxx(r)			
	Week 4 (Visit 4)	N	N	N	N		
Mean (SEM)		Mean (SEM)	Mean (SEM)	Mean (SEM)			
Median		Median	Median	Median			

Table 4.1  
Secondary Outcome Variable: Body Weight (Visit 3, 4, 5, 6) Descriptive Statistics and P-values

Parameter	Week	Control	TSFL	MEDD	Intervention p-value^
		Q1, Q3	Q1, Q3	Q1, Q3	
		Min, Max	Min, Max	Min, Max	
	Change (Week 4)	N	N	N	
		Mean (SEM)	Mean (SEM)	Mean (SEM)	
		Median	Median	Median	
		Q1, Q3	Q1, Q3	Q1, Q3	
		Min, Max	Min, Max	Min, Max	
		Within group p-value+	x.xxx(r)	x.xxx(r)	
		LS Mean (SEM)	LS Mean (SEM)	LS Mean (SEM)	x.xxx(r)
		Group comparison p-value*		x.xxx(r)	
	% Change (Week 4)	N	N	N	
		Mean (SEM)	Mean (SEM)	Mean (SEM)	
		Median	Median	Median	
		Q1, Q3	Q1, Q3	Q1, Q3	
		Min, Max	Min, Max	Min, Max	
		Within group p-value+	x.xxx(r)	x.xxx(r)	
		LS Mean (SEM)	LS Mean (SEM)	LS Mean (SEM)	x.xxx(r)
		Group comparison p-value*		x.xxx(r)	
	Week 8	N	N	N	
	(Visit 5)	Mean (SEM)	Mean (SEM)	Mean (SEM)	
		Median	Median	Median	
		Q1, Q3	Q1, Q3	Q1, Q3	
		Min, Max	Min, Max	Min, Max	
	Change (Week 8)	N	N	N	
		Mean (SEM)	Mean (SEM)	Mean (SEM)	
		Median	Median	Median	
		Q1, Q3	Q1, Q3	Q1, Q3	
		Min, Max	Min, Max	Min, Max	
		Within group p-value+	x.xxx(r)	x.xxx(r)	

Table 4.1  
Secondary Outcome Variable: Body Weight (Visit 3, 4, 5, 6) Descriptive Statistics and P-values

Parameter	Week	Control	TSFL	MEDD	Intervention p-value^
		LS Mean (SEM)	LS Mean (SEM)	LS Mean (SEM)	x.xxx(r)
		Group comparison p-value*		x.xxx(r)	x.xxx(r)
	% Change (Week 8)	N	N	N	
		Mean (SEM)	Mean (SEM)	Mean (SEM)	
		Median	Median	Median	
		Q1, Q3	Q1, Q3	Q1, Q3	
		Min, Max	Min, Max	Min, Max	
		Within group p-value+	x.xxx(r)	x.xxx(r)	x.xxx(r)
		LS Mean (SEM)	LS Mean (SEM)	LS Mean (SEM)	x.xxx(r)
		Group comparison p-value*		x.xxx(r)	
	Week 12	N	N	N	
	(Visit 6)	Mean (SEM)	Mean (SEM)	Mean (SEM)	
		Median	Median	Median	
		Q1, Q3	Q1, Q3	Q1, Q3	
		Min, Max	Min, Max	Min, Max	
	Change (Week 12)	N	N	N	
		Mean (SEM)	Mean (SEM)	Mean (SEM)	
		Median	Median	Median	
		Q1, Q3	Q1, Q3	Q1, Q3	
		Min, Max	Min, Max	Min, Max	
		Within group p-value+	x.xxx(r)	x.xxx(r)	x.xxx(r)
		LS Mean (SEM)	LS Mean (SEM)	LS Mean (SEM)	x.xxx(r)
		Group comparison p-value*		x.xxx(r)	
	% Change (Week 12)	N	N	N	
		Mean (SEM)	Mean (SEM)	Mean (SEM)	
		Median	Median	Median	
		Q1, Q3	Q1, Q3	Q1, Q3	
		Min, Max	Min, Max	Min, Max	
		Within group p-value+	x.xxx(r)	x.xxx(r)	x.xxx(r)

Table 4.1  
 Secondary Outcome Variable: Body Weight (Visit 3, 4, 5, 6) Descriptive Statistics and P-values

Parameter	Week	Control	TSFL	MEDD	Intervention p-value ^
	LS Mean (SEM)	LS Mean (SEM)	LS Mean (SEM)	LS Mean (SEM)	x.xxx(r)
	Group comparison p-value*		x.xxx(r)	x.xxx(r)	

^ p-values are from ANCOVA models, adjusted for sex and baseline values at Visit 2

(r) indicates rank transformation was employed.

\* p-values are adjusted for multiple comparisons (each active group vs. control group)

+ p-values are generated from paired t-test or sign-rank test, as appropriate

Table 4.2  
Secondary Outcome Variables: Weight Loss  $\geq 5\%$  and  $\geq 10\%$  (Visits 3, 4, 5, 6, 7)

Parameter	Week	Control	TSFL	MEDD	Intervention p-value ^	
Weight Loss responders (% change <math>\geq 5\%</math>)	% Change Week 2 (Visit 3)	N (%)	N (%)	N (%)	x.xxx	
	Group comparison p-value*		x.xxx	x.xxx		
	% Change Week 4 (Visit 4)	N (%)	N (%)	N (%)	x.xxx	
	Group comparison p-value*		x.xxx	x.xxx		
	% Change Week 8 (Visit 5)	N (%)	N (%)	N (%)	x.xxx	
	Group comparison p-value*		x.xxx	x.xxx		
	% Change Week 12 (Visit 6)	N (%)	N (%)	N (%)	x.xxx	
	Group comparison p-value*		x.xxx	x.xxx		
	% Change Week 16 (Visit 7)	N (%)	N (%)	N (%)	x.xxx	
	Group comparison p-value*		x.xxx	x.xxx		
	Weight Loss responders (% change <math>\geq 10\%</math>)	% Change Week 2 (Visit 3)	N (%)	N (%)	N (%)	x.xxx
		Group comparison p-value*		x.xxx	x.xxx	
		% Change Week 4 (Visit 4)	N (%)	N (%)	N (%)	x.xxx
		Group comparison p-value*		x.xxx	x.xxx	
% Change Week 8 (Visit 5)		N (%)	N (%)	N (%)	x.xxx	
Group comparison p-value*			x.xxx	x.xxx		
% Change Week 12 (Visit 6)		N (%)	N (%)	N (%)	x.xxx	
Group comparison p-value*			x.xxx	x.xxx		
% Change Week 16 (Visit 7)		N (%)	N (%)	N (%)	x.xxx	
Group comparison p-value*			x.xxx	x.xxx		

^ p-values are from GLM models with a logit link and binomial distribution specified and sex as a covariate

\* p-values are adjusted for multiple comparisons (each active group vs. control group)

Table 4.3  
Secondary Outcome Variable: Body Composition (Visits 4, 5, 6, 7) Descriptive Statistics and P-values

Parameter	Week	Control	TSFL	MEDD	Intervention p-value^	
Total Fat Mass (kg)	Baseline ( Week 0) (Visit 2)	N	N	N	N	
		Mean (SEM)	Mean (SEM)	Mean (SEM)	Mean (SEM)	
		Median	Median	Median	Median	
		Q1, Q3	Q1, Q3	Q1, Q3	Q1, Q3	
		Min, Max	Min, Max	Min, Max	Min, Max	
	Week 4 (Visit 4)	N	N	N	N	
		Mean (SEM)	Mean (SEM)	Mean (SEM)	Mean (SEM)	
